2.10 STUDY TIMELINES AND MILESTONES

**Timelines and Milestones**: Infrastructure and regulatory requirements should be completed by ≤ 6 months after funding is awarded (Table 3). The personnel of this project have considerable clinical trial experience. Our potential subject population is so many times greater than the necessary study numbers that we anticipate being able to meet our target goal enrollment before the end of the project duration.

		Y	EAR 1		YEAR 2				
	Q1	Q2	Q3	Q4	Q1	Q2	Q3	Q4	
Regulatory/Admin Issues	x	x							
Subject Recruitments (#)			3	4	5	4	2		
Data Analysis and Reporting									

Table 3. Anticipated enrollment and key study milestones.

3 HUMAN SUBJECTS

3.1 SUBJECT POPULATION

Human Subject Characteristics:

The study population will be eighteen (18) adult patients with COPD and autoantibodies against GRP78. The subjects will be recruited from the clinics or registries of the Lung Health Center (LHC) at the University of Alabama at Birmingham (UAB). The trial subjects must provide written informed consent prior to participation. Surrogate consent will not be allowed. No special vulnerable populations will be studied.

The demographics of the study population will reflect the characteristics of patients who suffer from COPDand are evaluated at at the University of Alabama at Birmingham (UAB) clinics and LHC.. These will be older patients (COPD is predominantly a disease of mature and elderly individuals). The ethnicities of the subjects will similarly reflect the demographics of our clinic populations that are afflicted with this disease. We anticipate that our recruited population will be 50% female, 75% Caucasian and 25% African American)

Recruitment goals (~9 subjects/year) are easily feasible, based on the large number of potential participants available here at UAB.. This pulmonary clinics at this academic medical center

routinely sees hundreds of new patients annually, and the majority of these have COPD. The UAB LHC has a long history of success in the recruitment and retention of participants in various studies, and has routinely been among the top recruitment sites in several large, NIH funded, multicenter clinical trials. A full time recruiter is employed at the LHC, who relies on in-clinic contact with potential participants, as well as print, television, and media advertising, as needed. There are currently over 1000 patients with COPD in the LHC databases and several hundred in the active research registries of the Center.

3.1.1 Inclusion of Women and Minorities

Women who meet the inclusion criteria, and have none of the exclusion criteria, will be enrolled without restriction as dictated by the study protocols. Because of the use of a study medication, woman of child bearing potential must meet specialized inclusion/exclusion criteria to minimize this risk. We will make efforts to enroll participants in this research in a distribution that mirrors the clinic population at our center (50% female, 75% Caucasian and 25% African American)..

3.1.2 Inclusion of Children

Children under 18 years of age will not be enrolled because they do not develop this disease.

3.2 INCLUSION AND EXCLUSION CRITERIA

The inclusion criteria have been selected to study a patient population with COPD and autoimmunity. The exclusion criteria are selected to exclude patients with increased risk for the experimental intervention.

Inclusion Criteria

1.) A history of past tobacco smoking (\geq 10 pack years), but quit for \geq 6 months at the time of enrollment. Smoking cessation will be confirmed by serum cotinine assays.

2.) Clinical diagnosis of at least moderate COPD as defined by the Global Initiative for Obstructive Lung Disease (GOLD) criteria:

- a. Post bronchodilator FEV₁/FVC < 70%,
- b. Post bronchodilator FEV₁ between 25% and 80% predicted, with or without chronic symptoms (i.e., cough, sputum production).

COPD

3.) Ability and willingness to give informed consent.

4.) Levels of plasma autoantibodies that have specifities against a 15–mer peptide sequence within the GRP78 molecule (aa. 246-260) that are in the upper three quartiles of values present in COPD patients. We have discovered that circulating levels of IgG autoantibodies with avidity against this peptide (GRP78 Peptide 25) are associated with the magnitude of carotid artery intimal medial thickness (IMT) among COPD patients (Figure 5). Limiting enrollments to subjects with readily detectible autoantibodies (e.g., those with levels in the 25th percentile or above) will easily enable us to ascertain if the experimental treatment (belimumab) results in a significant reduction of these autoantibodies.

5.) Age 40-75 y.o. COPD is a disease of older individuals.

Exclusion Criteria

1.) History of prior acute COPD exacerbations or no more than one moderate exacerbation in the last year and no exacerbations four months prior to enrollment. A past history of an acute exacerbation is the single biggest risk for recurrence.³⁶ Exclusion of these higher-risk subjects will minimize drop-outs.

2.) Oral steroids or cellular immunosuppressant use (e.g., cyclophosphamide) within 6 months.

3.) History or clinical or laboratory evidence of other autoimmune syndromes.

4.) Inability or unwillingness to complete the treatment and surveillance protocols.

5.) Eligible for lung transplant at time of enrollment. This exclusion will mitigate any potential, however slight, that a patient could be rejected for transplantation due to surgeon concerns about this novel therapy (and will also obviate early drop-outs due to transplantation).

6.) History of malignant neoplasm within the last 5 years.

7.) Evidence of serious suicide risk including any history of suicidal behavior in the last 6 months and/or any suicidal ideation in the last 2 months or those, in the investigator's judgment, pose a significant suicide risk.

8.) History of a primary immunodeficiency.

9.) Significant IgG deficiency (IgG level < 400 mg/dL).

10.) Have an IgA deficiency (IgA level < 10 mg/dL).

11.) Currently on any suppressive therapy for a chronic infection (such as tuberculosis, pneumocystis, cytomegalovirus, herpes simplex virus, herpes zoster or atypical mycobacteria).

12.) Hospitalization for treatment of infection within 60 days of screening.

13.) Use of parenteral (IV or IM) antibiotics (antibacterials, antivirals, anti-fungals, or anti-parasitic agents) within 60 days of screening.

14.) Current drug or alcohol abuse or dependence, or a history of drug or alcohol abuse or dependence within 365 days prior to screening.

15.) History of a positive HIV test or positive screening test for HIV.

16.) Serologic evidence of current or past Hepatitis B (HB) or Hepatitis C (HC) infection based on positive tests for HBsAg or HBcAb, or HCAb.

17.) History of an anaphylactic reaction to parenteral administration of contrast agents, human or murine proteins or monoclonal antibodies.

18.) Any other clinically significant abnormal laboratory value in the opinion of the investigator.

19.) Any intercurrent significant medical or psychiatric illness that the investigator considers would make the candidate unsuitable for the study.

20.) Women of Child Bearing Potential (WCBP) must have a negative urine pregnancy test at screening, and agree to 1 of the following:

Complete abstinence from intercourse from 2 weeks prior to administration of the 1st dose of study agent until 16 weeks after the last dose of study agent (Sexual inactivity by abstinence must be consistent with the preferred and usual lifestyle of the subject. Periodic abstinence (e.g. calendar, ovulation, symptothermal, post-ovulation methods) and withdrawal are not acceptable methods of contraception)

OR

Consistent and correct use of 1 of the following acceptable methods of birth control for 1 month prior to the start of the study agent, during the study, and 16 weeks after the last dose of study agent:

- Oral contraceptive, either combined or progestogen alone
- Injectable progestogen
- Implants of levonorgestrel or etonogestrel
- Estrogenic vaginal ring
- Percutaneous contraceptive patches
- Intrauterine device (IUD) or intrauterine system (IUS) with <1% failure rate as stated in the product label
- Male partner sterilization (vasectomy with documentation of azoospermia) prior to the female subject's entry into the study, and this male is the sole partner for that subject. For this definition, "documented" refers to the outcome of the investigator's/designee's medical examination of the subject or review of the subject's medical history for study eligibility, as obtained via a verbal interview with the subject or from the subject's medical records
- Double barrier method: condom and occlusive cap (diaphragm or cervical/vault caps) plus spermicidal agent (foam/gel/film/cream/suppository)

21.) Use of Excluded Medications:

- Anti-B-cell therapy:
 - Wash out of 5 therapeutic half lives after prior B-cell therapy, or until pharmacodynamic effect would be minimal (e.g., 1 year following rituximab)
- 365 days Prior to Belimumab:
 - Any biologic investigational agent (e.g., abetimus sodium, anti CD40L antibody, BG9588/ IDEC 131)
- Investigational agent applies to any drug not approved for sale in the country in which it is being used

- 30 Days Prior to Belimumab (or 5 half lives, whichever is greater)
 - o Any non-biologic investigational agent
- Investigational agent applies to any drug not approved for sale in the country in which it is being use
- Live vaccines within 30 days prior to baseline or concurrently with belimumab

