	2.) Arm 2: Placebo Controls (n = 6) . These subjects will be treated with identically appearing placebo i.v. on the same schedule as the experimental arm subjects (i.e., three "loading" doses, two weeks apart, followed by five more monthly infusions. Again, the final assessment will be performed at month 7 ($210+10$ days after treatment start).
Planned Sample Size:	A total of 18 subjects will be enrolled in this trial. In order to reach the needed sample size of 18, twenty-five subjects will be randomized to account for subjects who have been withdrawn early due to the current COVID-19 pandemic in order to comply with guidance regarding human subjects research conduct and also for medical reasons un-related to study drug or study procedures.
Duration of Treatment:	Six months
Duration of Participation	Ten months
Inclusion Criteria:	 A history of past tobacco smoking (≥10 pack years), but quit for ≥6 months at the time of enrollment. Smoking cessation will be confirmed by serum cotinine assays.
	2.) Clinical diagnosis of at least moderate COPD as defined by the Global Initiative for Obstructive Lung Disease (GOLD) criteria:

	 a. Post bronchodilator FEV₁/FVC < 70%, b. Post bronchodilator FEV₁ between 25% and 80% predicted, with or without chronic symptoms (i.e., cough, sputum production). COPD
	3.) Ability and willingness to give informed consent.
	4.) Levels of plasma autoantibodies against a 15–mer peptide sequence within the GRP78 molecule (a.a. 246-260) that are in the upper three quartiles of values present in COPD patients. This epitope will henceforth be denoted as GRP78 Peptide 25. Levels of anti-GRP78 Peptide 25 autoantibodies are significantly correlated with carotid artery intimal medial thickness (IMT) among COPDpatients.
	5.) Age 40-75 y.o. COPD is a disease of older individuals.
Major Exclusion Criteria:	1.) History of more than one moderate (treated as outpatient) or severe (requiring hospitalization) acute exacerbation of COPD within the 12 months prior to screening or any moderate or severe exacerbation within the 4 months prior to screening. A past history of an acute exacerbation is the single biggest risk for recurrence. ³⁶ Exclusion of subjects at highest risk will minimize dropouts.
	2.) Oral steroids or cellular immunosuppressant use (e.g., cyclophosphamide) within 6 months.
	3.) History or clinical or laboratory evidence of other autoimmune syndromes (confirmed by self-report and medical record review).

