	4.) Inability or unwillingness to complete the treatment and surveillance protocols.
	5.) Listed for lung transplant at time of enrollment. This exclusion will mitigate any potential, however slight, that a patient could be rejected for transplantation due to surgeon concerns about this novel therapy (and will also obviate early drop-outs due to transplantation).
	6.) History of malignant neoplasm within the last 5 years.
	7.) Evidence of serious suicide risk including any history of suicidal behavior in the last 6 months and/or any suicidal ideation in the last 2 months or those, in the investigator's judgment, pose a significant suicide risk.
	8.) History of a primary immunodeficiency.
	9.) Significant IgG deficiency (IgG level < 400 mg/dL).
	10.) IgA deficiency (IgA level < 10 mg/dL).
	11.) Currently on any suppressive therapy for a chronic infection (such as tuberculosis, pneumocystis, cytomegalovirus, herpes simplex virus, herpes zoster or atypical mycobacteria).

12.) Hospitalization for treatment of infection within 60 days of screening.
13.) Use of parenteral (IV or IM) antibiotics (antibacterials, antivirals, anti- fungals, or anti-parasitic agents) within 60 days of screening.
14.) Current drug or alcohol abuse or dependence, or a history of drug or alcohol abuse or dependence within 365 days prior to Day 0 (for compliance and safety).
15.) History of a positive HIV test or positive screening test for HIV.
16.) Serologic evidence of current or past Hepatitis B (HB) or Hepatitis C (HC) infection based on positive tests for HBsAg or HBcAb, or HCAb.
17.) History of an anaphylactic reaction to parenteral administration of contrast agents, human or murine proteins or monoclonal antibodies.
18.) Any other clinically significant abnormal laboratory value in the opinion of the investigator.
19.) Any intercurrent significant medical or psychiatric illness that the investigator considers would make the candidate unsuitable for the study.
20.) Women of Child Bearing Potential (WCBP) must have a negative urine pregnancy test at screening, and agree to 1 of the following:

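### Exclusions 1 (exacerbations) and 5 (lung transplant) are stated differently in the synopsis and in section 3.2, and the protocol does not say which text governs

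*Combined protocol and SAP*

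**What the plan says.** The synopsis, under Major Exclusion Criteria, and section 3.2 each carry a list of 21 numbered exclusions.

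**Exclusion 1.** The synopsis excludes a "History of more than one moderate (treated as outpatient) or severe (requiring hospitalization) acute exacerbation of COPD within the 12 months prior to screening", and also "any moderate or severe exacerbation within the 4 months prior to screening". Section 3.2 has "History of prior acute COPD exacerbations or no more than one moderate exacerbation in the last year and no exacerbations four months prior" to enrollment, and explains the purpose as "Exclusion of these higher-risk subjects will minimize drop-outs". Section 2.9.1 (Specific Aim 1, Potential Pitfalls) describes the same exclusion a third way: patients with a history of exacerbations are kept out, with no count, severity or time window.

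**Exclusion 5.** The synopsis has "Listed for lung transplant at time of enrollment". Section 3.2 has "Eligible for lung transplant at time of enrollment". The rationale sentence that follows is the same in both.

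**Exclusion 14.** For drug or alcohol abuse, the synopsis looks back "within 365 days prior to Day 0 (for compliance and safety". Section 3.2 counts the 365 days back from screening.

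**Which list applies.** Sections 2.3 and 2.6.1 require patients to meet all the criteria but point to neither list. Section 5.6.4 then reuses the criteria during follow-up: a subject who acquires a condition or status that would have been an exclusion is terminated from the trial.

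**The concern.** These are operative rules, not background. A coordinator holding a patient's history has to say yes or no, and the answer can depend on which page is open. In section 3.2, exclusion 1 is also defective in itself. It places acceptable histories (at most one moderate event, none recently) among the reasons to exclude, which is the reverse of its purpose sentence.

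At stake are a reproducible definition of the trial population, the ability to verify eligibility and audit compliance (sections 5.5.1 and 6.6), and a clear trigger for the termination rule in section 5.6.4. Section 3.2 ties the exclusions to patients at increased risk from the intervention, so the ambiguity concerns rules written partly for safety.

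**Working it through.** No figure in the plan bears on this, so the check is a comparison of the texts.

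**Step 1: count the differences.** Comparing items 1 to 21 and ignoring case, spacing and punctuation, the wording differs in five: 1, 3, 5, 10 and 14. Item 10 differs only in two opening words. Item 3 excludes the same status in both lists, and the synopsis merely adds how it is confirmed. That leaves 5 − 2 = 3 exclusions that differ in substance (1, 5, 14) and 21 − 3 = 18 that state the same rule. The five inclusion criteria agree in substance.

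**Step 2: exclusion 1, element by element.**

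| Element | Synopsis | Section 3.2 |
|---|---|---|
| Look-back | 12 months and 4 months | First clause has no limit; later clauses one year and four months |
| Severity, 12 months | Moderate or severe, more than one | Allowance names only a moderate event |
| Severity, 4 months | Moderate or severe | None named |
| Reference date (4 months) | Screening | Enrollment: "no exacerbations four months prior to enrollment" |
| Logic | Lists disqualifying histories | Mixes a disqualifying history with permitted ones |

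**Step 3: apply each text to example patients.** Consider exclusion 1 alone. Take screening and enrollment on the same day, so that the reference date plays no part. The fourth column repairs section 3.2 by reading its *or* as *unless*.

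| History | Synopsis | 3.2, literal | 3.2, repaired | 2.9.1 |
|---|---|---|---|---|
| No exacerbation ever | Not excluded | Excluded | Not excluded | Not excluded |
| One moderate event, 3 years ago | Not excluded | Excluded | Not excluded | Excluded |
| One moderate event, 8 months ago | Not excluded | Excluded | Not excluded | Excluded |
| One severe event, 8 months ago | Depends on whether *more than one* also governs severe events | Excluded | Unsettled: allowance names only moderate | Excluded |
| Event below moderate, 2 months ago | Not excluded | Excluded | Excluded | Excluded |

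The literal column excludes every row. Anyone with a past event meets the first clause, and anyone without one meets the second. The literal text therefore cannot work as an entry rule, and the reader has to repair it without guidance. The repaired reading still parts from the synopsis on the mild event and leaves the severe one open.

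**Step 4: the reference date.** If screening and enrollment fall on different days, a moderate event between them lies inside the four-month window of section 3.2 but outside that of the synopsis. A moderate event just under four months before screening can be caught by the synopsis clause and be too old for the one in section 3.2. How often this matters depends on the interval between the two dates, which the documents do not give; nor do they define enrollment.

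**Step 5: exclusion 5.** A patient who is eligible for transplant but not listed passes the synopsis and fails section 3.2.

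**Step 6: exclusion 14.** Tables 1 and 2 start treatment on Day 1, and the schedule contains no Day 0. The synopsis therefore counts back from a day that does not exist in the schedule.

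**Step 7: precedence.** The supplied text contains no rule that the synopsis or the body prevails, and no amendment log by which either wording could be set aside as superseded.

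**The case against.** The strongest defence is that the intent is plain. The synopsis version of exclusion 1 is clear, the version in section 3.2 is a drafting slip, and staff would have applied the sensible rule. Exclusion 2, identical in both lists, bars oral steroid use within 6 months, so a recent exacerbation treated that way is excluded under any text. The mild-event case is thin, because the protocol describes moderate and severe events but no lesser category. An event between screening and enrollment might also be caught by exclusion 19, the investigator's judgment on intercurrent illness.

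Much of this stands, and it narrows the practical gap. It does not close it. Exclusion 2 does not settle a single severe event 6 to 12 months back. Nothing in it touches exclusion 5, where both wordings are clear and name different groups.

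A reader might say that the heading of the synopsis list marks it as a summary that yields to the body. But that list runs through the same 21 items and does not defer to section 3.2, and letting the body prevail would select the text whose logic is inverted.

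A reader might also infer a breach of the commitment in section 6.2.1 to a single protocol version. That is a version-control duty and does not address inconsistency inside one version.

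**Conclusion.** The point holds as an internal inconsistency, and the text of exclusion 1 in section 3.2 is wrong as written. Exclusions 1 and 5 admit different patients depending on the list used. Exclusion 14 differs in a minor way, and exclusion 3 only in a confirmation step. The extent is 3 of 21 exclusions. The number of subjects affected is not in the documents and cannot be estimated from them. It should be fixed, and it warrants no higher rating than that.

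Three stronger conclusions are tempting but unsupported:

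- **Ineligible patients were enrolled.** The documents contain no screening outcomes, so this is unknown.
- **The treatment comparison is biased or power is lost.** Eligibility is settled before randomization (sections 2.3 and 2.6.1), so an ambiguous entry rule applies to both arms alike, and the sample-size calculation does not depend on it.
- **Retention has been affected through section 5.6.4.** The wording makes this possible: a subject who becomes eligible for transplant without being listed would meet one version and not the other. But both versions of exclusion 5 refer to the time of enrollment, Table 2 schedules no transplant reassessment, and exacerbations on study have their own rule in section 5.6.4.

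The conclusion assumes that the pages not available for review contain no precedence statement.

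**What to change.** - **Exclusions 1 and 5.** Reconcile the synopsis, section 2.9.1 and section 3.2, and put one identical text in both lists. Word exclusion 1 as a true exclusion, with one look-back rule, one reference date and an explicit statement of which severities count, including a single severe event. Use one transplant term in exclusion 5. The sponsor chooses the clinical rule in each case; this review takes no position on it.
- **Exclusion 14.** Give it one reference date that exists in the schedule.
- **Section 5.6.4.** State how the general termination sentence applies to the reconciled exclusions 1 and 5, alongside the specific rule for exacerbations on study.
- **Record check.** From existing screening records, report how many randomized subjects the two versions classify differently. The synopsis foresees 25 randomized, so the task is small, and it shows whether the ambiguity affected anyone.

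The cost is amendment wording and a review of records already held. No new procedure, visit or assay is needed.

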4 RECRUITMENT AND INFORMED CONSENT PROCEDURES

4.1 RECRUITMENT METHODS

Subjects will be recruited from the outpatient population followed at The Kirklin Clinic and UAB LHC. The primary care physician/clinical care team, who may be study investigators or colleagues of the study investigators, will first identify potential research subjects. The clinician investigators will discuss the research project with the potential subjects.

